12.5.3 Patient reported outcomes

L-IPF (Impacts and Symptoms Modules), K-BILD, Leicester cough, and R-Scale for IPF questionnaires score will be reported by treatment group, patients, and epoch/visit/time. Summary statistics on the change from baseline of PRO score at the end of the treatment epoch will be provided by treatment and visit time.

12.6 Analysis of exploratory endpoints

12.6.1 Efficacy and/or Pharmacodynamic endpoint(s)

Disease exacerbation

Time to IPF exacerbations or suspected exacerbations will be assessed using the statistical method mentioned in [Section 12.5.1](#) “Time to event analysis”. In addition, number and percentage of exacerbations will be summarized by epoch/visit/treatment.

Exploratory Progression-free survival (PFS)

Time to progression as defined by a composite endpoint including any of the following events:

- Absolute reduction from baseline of $\geq 5\%$ predicted in FVC
- Non elective hospitalization for respiratory events
- Lung transplant or death

Same statistical analysis specified in [Section 12.5.1](#) “Time to event analysis” will be applied to this endpoint.

Pulmonary imaging

Change from baseline to the end of treatment epoch (26 weeks of treatment) in quantitative high-resolution computed tomography (qHRCT) structural and functional metrics (interstitial fibrotic features) will be reported using summary statistics by treatment.

12.6.2 Pharmacokinetics

In order to assess the pharmacokinetics of the investigational products after multiple doses, investigational product concentrations will be measured.

Concentration data for each analyte in a cohort will be listed by treatment, subject, and epoch/visit/sampling time point. Descriptive summary statistics may be provided by visit, treatment and visit/sampling time point, including the frequency (n, %) of concentrations below the LLOQ and reported as zero.

Summary statistics may include mean (arithmetic and geometric), standard deviation (SD), coefficient of variation (CV) (arithmetic and geometric), median, minimum and maximum. Concentrations below LLOQ will be treated as zero in summary statistics and for PK parameter calculations. A geometric mean will not be reported if the dataset includes zero values.

Cohort specific pharmacokinetic parameters will be calculated as described in [Section 17](#).

Graphical presentation may be provided in addition.

12.6.3 PK/PD relationships

Relationships between PK and PD variables may be explored using population PK. Additional statistical analysis such as analysis of variance (ANOVA) or regression analysis may be performed, if necessary.

Modeling of the PK and PD data may be performed as appropriate. As the PK and PD data from the current study may be pooled with data from previous studies, the PK/PD analysis will be described and reported separately in a modeling plan and modelling report respectively.

12.6.4 Biomarkers

Change from baseline in soluble markers (which may include but are not limited to **CCI**) in the peripheral blood and protein profiling to explore the markers reflecting the treatment response will be reported using summary statistics by epoch and treatment.

For all biomarker data (as applicable) summary statistics will be provided by cohort, treatment group and visit/time. As applicable, values above the upper limit of quantification (ULOQ) will be imputed as ULOQ in graphical summaries (with a special symbol) and for the calculation of the summary statistics, and values below the lower limit of quantification (LLOQ) will be imputed as LLOQ/2 for these analyses. The number of values outside of the limits of quantification will be reported in each table. All biomarker data, change from the baseline, percent change from baseline will be listed by cohort, treatment group, participants, and visit/time. Graphical summaries (including spaghetti plots, boxplots, and mean plots with SD) may be provided by treatment and visit/time. Values below the LLOQ will be imputed as LLOQ/2 for these analyses. The number of values outside of the limits of quantification will be reported in each table.

CCI [REDACTED]
[REDACTED]
[REDACTED].

12.6.5 DNA

Exploratory DNA studies are designed to investigate the association between genetic factors (genotypes) and clinical assessments (phenotypes) which are collected during the clinical trial. Without prior evidence of a strong association, a number of possible associations are evaluated with exploratory analyses. A range of statistical tests are used for the analyses. Additional data, from other clinical trials, are often needed to confirm associations. Alternatively, if the number of participants enrolled in the study is too small to complete proper statistical analyses, the data may be combined, as appropriate, with those from other studies to enlarge the dataset for analysis.

Data generated on hypothesis-free platforms will be reported separately (e.g. CSR addendum).

12.7 Interim analyses

In addition to those listed below, other interim analyses may be conducted to support decision making concerning the current clinical study, the sponsor's clinical development projects in general or in case of any safety concerns.

12.7.1 Cohort Completion Analyses

Data will be analyzed at the completion of each cohort in the trial.

Cohort completion analyses are planned when participants complete each cohort (End of Treatment). The unblinded analysis results including efficacy and safety assessment will be reviewed by the clinical team and further shared with Novartis teams and members of the DMC. The data will be used to determine if the noted efficacy was sufficient to allow early transition of the respective IP to a later stage study.

12.7.2 Within each cohort

Interim analyses are planned when sufficient participants complete their 26-week post-treatment assessments in each cohort (approximately 50%). Data from participants who have completed their 26-week post-treatment assessment and data from participants who have not completed the treatment epoch but have post-treatment assessments at the time of the IA will be included. The purpose of this unblinded IA is to assess early efficacy and to assess futility. The key endpoint to be evaluated at this IA will be the change from baseline in FVC %predicted.

There will be no pause in enrollment at the time of interim analysis, and participants may continue to be enrolled until the interim analysis is complete.

The Bayesian posterior probability of the treatment effect (treatment – placebo) will be calculated for the endpoint. If there is more than 60% probability that the treatment effect at the end of treatment epoch (26 weeks of treatment) is <0 (treatment worse than placebo), then this will act as evidence to suggest that the investigational product has not had a beneficial effect on the endpoint in this population. This data, together with other key endpoints, will be used to assess whether the cohort could be stopped for futility.

Similarly, if there is enough information at this interim analysis to conclude that there is 90% posterior probability that the treatment effect is >0 (treatment better than placebo) in the endpoint, and there is 50% posterior probability of the treatment effect $> 1.3\%$, then this information, together with other key endpoints, will be used to consider early evidence of efficacy and decision of launching later stage of the clinical trials for the respective investigational product.

If the study is not stopped for futility or for early evidence of efficacy at the time of the IA, the cohort will continue until all participants have completed the cohort.

Within cohort IAs, unblinded interim analysis results will be reviewed by the clinical team. The clinical team may communicate interim results (e.g. evaluation of efficacy criteria or information needed for planning/modifying another study) to relevant Novartis teams and members of the DMC.

No further dissemination of interim results should occur, in particular not with individuals involved in treating the study's participants or assessing clinical data (e.g. ECGs, images, symptoms) obtained in the study.

12.8 Sample size calculation

12.8.1 Primary endpoint(s)

Without considering the drop-off rate, 40 participants per active treatment group and at least 40 participants on placebo of each cohort will give at least 80% power to detect a treatment improvement in change from baseline in FVC%_p (treatment – placebo) for at least 2% in patients with IPF assuming the standard deviation is around 5%.

The sample size calculation is based on the primary efficacy endpoint of change from baseline in FVC%_p at week 26. The criteria for this calculation aimed for a 90% level of proof that difference in change in FVC%_p from baseline to week 26 between treatment and placebo and the mean treatment effect is at least 1.3% better than placebo effect with 50% probability. The former targets proof that the treatment produces a statistically significant improvement in change from baseline in FVC, while the latter targets proof of clinical relevance.

The sample size calculation also takes into account the interim analysis step with futility and early efficacy criteria defined in [Section 12.7](#). The overall type I error at the end of study will be approximately 13%.

Additional participants may be enrolled if more than 15% of the planned randomized participants have not completed the 26 weeks of treatment, as per protocol requirements. Prior to enrolling additional participants, a DMC review of safety data will occur to ensure there are no tolerability/safety issues that would advise against enrolling additional participants.

Refer to [Section 17](#) for cohort specific sample size after considering drop off rate and randomization ratio between the treatment group and placebo group.

12.8.2 Secondary endpoint(s)

Not applicable.

13 Ethical considerations and administrative procedures

13.1 Regulatory and ethical compliance

This clinical study was designed and shall be implemented, executed, and reported in accordance with the ICH Harmonized Tripartite Guidelines for Good Clinical Practice, with applicable local regulations (including European Directive 2001/20/EC or European Clinical Trial Regulation 536/2014, US CFR 21), and with the ethical principles laid down in the Declaration of Helsinki.

13.2 Responsibilities of the investigator and IRB/IEC

Before initiating a trial, the investigator/institution must obtain approval/favorable opinion from the Institutional Review Board/Independent Ethics Committee (IRB/IEC) for the trial protocol, written informed consent form, consent form updates, participant recruitment procedures (e.g. advertisements) and any other written information to be provided to participants. Prior to study start, the investigator is required to sign a protocol signature page confirming his/her agreement to conduct the study in accordance with these documents and all of the instructions and procedures found in this protocol and to give access to all relevant data and records to Novartis monitors, auditors, Novartis Quality Assurance representatives, designated agents of Novartis, IRBs/IECs, and regulatory authorities as required. If an inspection of the clinical site is requested by a regulatory authority, the investigator must inform Novartis immediately that this request has been made.

13.3 Publication of study protocol and results

The protocol will be registered in a publicly accessible database such as clinicaltrials.gov and as required in EudraCT or CTIS public website. In addition, after cohort completion (defined as cohort last participant last visit) and finalization of the cohort study report the results of this trial will be submitted for publication and posted in a publicly accessible database of clinical trial results, such as the Novartis clinical trial results website and all required Health Authority websites (e.g. Clinicaltrials.gov, EudraCT or CTIS public website etc.).

Summary results of primary and secondary endpoints will be disclosed based upon the global Last Participant Last Visit (LPLV) date, since multinational studies are locked and reported based upon the global LPLV.

For details on the Novartis publication policy including authorship criteria, please refer to the Novartis publication policy training materials that were provided to you.

Any data analysis carried out independently by the Investigator must be submitted to Novartis before publication or presentation.

13.4 Quality Control and Quality Assurance

Novartis maintains a robust Quality Management System (QMS) that includes all activities involved in quality assurance and quality control, to ensure compliance with written Standard Operating Procedures as well as applicable global/local GCP regulations and ICH Guidelines.

Audits of investigator sites, vendors, and Novartis systems are performed by auditors, independent from those involved in conducting, monitoring, or performing quality control of the clinical trial. The clinical audit process uses a knowledge/risk-based approach.

Audits are conducted to assess GCP compliance with global and local regulatory requirements, protocols, and internal SOPs, and are performed according to written Novartis processes.

13.5 Participant Engagement

The following participant engagement initiatives are included in this study and will be provided, as available, for distribution to study participants. If compliance is impacted by cultural norms or local laws and regulations, sites may discuss modifications to these requirements with Novartis.

- Thank You card
- Treatment information
- Plain language trial summary

14 Protocol adherence

This protocol defines the study objectives, the study procedures, and the data to be collected on study participants. Additional assessments required to ensure safety of participants should be administered as deemed necessary on a case-by-case basis. Under no circumstances including incidental collection is an investigator allowed to collect additional data or conduct any additional procedures for any purpose involving any investigational drugs under the protocol, other than the purpose of the study. If despite this interdiction prohibition, data, information, observation would be incidentally collected, the investigator shall immediately disclose it to Novartis and not use it for any purpose other than the study, except for the appropriate monitoring on study participants.

Investigators ascertain they will apply due diligence to avoid protocol deviations. If an investigator feels a protocol deviation would improve the conduct of the study this must be considered a protocol amendment, and unless such an amendment is agreed upon by Novartis and approved by the IRB/IEC and Health Authorities, where required, it cannot be implemented.

16.1 Appendix 1: Liver event and laboratory trigger definitions & follow-up requirements

Table 16-1 Liver event and laboratory trigger definitions

	Definition/ threshold
Liver laboratory triggers If ALT, AST, and total bilirubin normal at baseline:	
• ALT or AST $> 5 \times$ ULN• ALP $> 2 \times$ ULN (in the absence of known bone pathology)• Total bilirubin $> 3 \times$ ULN (in the absence of known Gilbert syndrome)• ALT or AST $> 3 \times$ ULN and INR > 1.5• Potential Hy's Law cases (defined as ALT or AST $> 3 \times$ ULN and Total bilirubin $> 2 \times$ ULN [mainly conjugated fraction] without notable increase in ALP to $> 2 \times$ ULN)• Any clinical event of jaundice (or equivalent term)• ALT or AST $> 3 \times$ ULN accompanied by (general) malaise, fatigue, abdominal pain, nausea, or vomiting, or rash with eosinophilia• Any adverse event potentially indicative of a liver toxicity
If ALT or AST abnormal at baseline:	
• ALT or AST $> 3 \times$ baseline or > 300 U/L (whichever occurs first)

Table 16-2 Follow up requirements for liver laboratory triggers - ALT, AST, TBL

ALT	TBL	Liver Symptoms	Action
ALT increase without bilirubin increase:			
If normal at baseline: ALT > 3 x ULN	Normal For participants with Gilbert's syndrome: No change in baseline TBL	None	
 No change to study treatment Measure ALT, AST, ALP, GGT, TBIL, INR, albumin, CK, and GLDH in 48-72 hours. Follow-up for symptoms.
If elevated at baseline: ALT > 2 x baseline or > 300 U/L (whichever occurs first)			
If normal at baseline: ALT > 5 x ULN for more than two weeks	Normal For participants with Gilbert's syndrome: No change in baseline TBL	None	
 Measure ALT, AST, ALP, GGT, TBIL, INR, albumin, CK, and GLDH in 48-72 hours. Follow-up for symptoms. Initiate close monitoring and workup for competing etiologies. Study drug can be restarted only if another etiology is identified and liver enzymes return to baseline.
If elevated at baseline: ALT > 3 x baseline or > 300 U/L (whichever occurs first) for more than two weeks			
If normal at baseline: ALT > 8 x ULN	Normal	None	
ALT increase with bilirubin increase:			
If normal at baseline: ALT > 3 x ULN	TBL > 2 x ULN (or INR > 1.5) For participants with Gilbert's syndrome: Doubling of direct bilirubin	None	
If elevated at baseline: ALT > 2 x baseline or > 300 U/L (whichever occurs first)			
If normal at baseline: ALT > 3 x ULN			
 Discontinue study drug
If elevated at baseline: ALT > 2 x baseline or > 300 U/L (whichever occurs first)	Normal or elevated	Severe fatigue, nausea, vomiting, right upper quadrant pain	

Table 16-3 Isolated total bilirubin elevation

Criteria	Recommendation
Any elevation > ULN	Fractionate bilirubin, evaluate for cholestatic liver injury (ALP) or alternative causes of bilirubin elevation (e.g. disease progression [imaging]). Treat alternative causes according to local institutional guidelines.
Grade 2 (>1.5 – 3.0 ULN)	Maintain treatment. Repeat LFTs within 48-72 hours, then monitor LFTs weekly until resolution to ≤ Grade 1 or to baseline
Grade 3(>3.0 - 10 ULN)	Interrupt treatment. Repeat LFTs within 48-72 hours, then monitor LFTs weekly until resolution to ≤ Grade 1 or to baseline
Grade 4(>10 x ULN)	Discontinue study treatment

Based on investigator's discretion investigation(s) for contributing factors for the liver event can include serology tests, imaging and pathology assessments, hepatologist's consultancy; obtaining more detailed history of symptoms and prior or concurrent diseases, history of concomitant drug use, exclusion of underlying liver disease.

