10.2 Additional Safety Monitoring

10.2.1 Liver safety monitoring

To ensure participant safety and enhance reliability in determining the hepatotoxic potential of an investigational drug, a standardized process for identification, monitoring and evaluation of liver events has to be followed.

Please refer to [Table 16-1](#) in Appendix 2 for complete definitions of liver laboratory triggers.

Once a participant is exposed to study treatment, every liver event defined in [Table 16-2](#) should be followed up by the investigator or designated personnel at the trial site, as summarized below. Additional details on actions required in case of liver events are outlined in [Table 16-3](#). Repeat liver chemistry tests (i.e. ALT, AST, TBL, PT/INR, ALP and G-GT) to confirm elevation.

- These liver chemistry repeats will be performed using the central laboratory. If results will not be available from the central laboratory, then the repeats can also be performed at a local laboratory to monitor the safety of the participant. If a liver event is subsequently reported, any local liver chemistry tests previously conducted that are associated with this event should have results recorded on the appropriate CRF.
- If the initial elevation is confirmed, close observation of the participant will be initiated, including consideration of treatment interruption if deemed appropriate.
- Discontinuation of the investigational drug (refer to [Section 9.1.1](#)), if appropriate

- Hospitalization of the participant if appropriate
- Causality assessment of the liver event
- Thorough follow-up of the liver event should include
 - These investigations can include based on investigator's discretion: serology tests, imaging, and pathology assessments, hepatologist's consultancy; obtaining more detailed history of symptoms and prior or concurrent diseases, history of concomitant drug use, exclusion of underlying liver disease
 - Obtaining a more detailed history of symptoms and prior or concurrent diseases
 - Obtaining a history of concomitant drug use (including nonprescription medications and herbal and dietary supplement preparations), alcohol use, recreational use, and special diets
 - Imaging such as abdominal US, CT, or MRI, as appropriate
 - Obtaining a history of exposure to environmental chemical agents.
 - Considering gastroenterology or hepatology consultations.

All follow-up information and procedures performed must be recorded as appropriate in the CRF.

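### With normal baseline liver tests, AST above 3x ULN with ALT at or below 3x ULN can meet a potential Hy's Law or INR trigger in Table 16-1 yet match no row of the action table, so the visible core protocol sets no automatic stop

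*Protocol*

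**What the plan says.** Protocol Section 16.1 (Appendix 1) handles liver events in three tables.

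- **Table 16-1** defines the triggers. For participants with normal baseline ALT, AST and bilirubin, two are combined triggers. One is either transaminase above 3x ULN with INR above 1.5. The other is "Potential Hy's Law cases (defined as ALT or AST" above 3x ULN with total bilirubin above 2x ULN, mainly conjugated, and no ALP rise above 2x ULN).
- **Table 16-2** sets the actions: "Table 16-2 Follow up requirements for liver laboratory triggers - ALT, AST, TBL". Its columns are ALT, TBL, symptoms and action. Under the group heading "ALT increase with bilirubin increase", an ALT threshold is paired with "TBL > 2 x ULN (or INR > 1.5"). The action is "Discontinue study drug".
- **Table 16-3** is confined by its title: "Table 16-3 Isolated total bilirubin elevation". For bilirubin above 1.5 and up to 3.0 times ULN it says "Maintain treatment. Repeat LFTs within 48-72 hours".

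Section 10.2.1 tells sites how to use these tables. It sends the reader to Table 16-1 "in Appendix 2 for complete definitions of liver laboratory triggers", although Appendix 2 is the renal appendix. It ties follow-up to the events defined in Table 16-2 and names Table 16-3 for further detail on actions. Section 9.1.1 includes liver events among the reasons for required discontinuation, but only by referring back to Appendix 1.

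**The concern.** A trigger table and its action table should cover the same events. Here the trigger table accepts either transaminase, while the action table, despite its title, tests only ALT. The two triggers affected are serious ones: a transaminase rise together with signs of impaired liver function.

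Section 4.5 offers the pre-specified liver events as one of the trial's safety measures. For these two triggers, whether a site has a firm rule depends only on which transaminase crosses 3x ULN. Table 16-2 is also core text. Under the introduction to Section 17, it applies unchanged to any cohort that has no liver rule of its own.

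**Working it through.** No figure in the plan needs reproducing. The check applies the tables as rules to mirrored cases.

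**Inputs.** Table 16-1: the two combined triggers above. Table 16-2: the normal-baseline ALT criteria, which are above 3x ULN (no bilirubin rise, no symptoms), above 5x for more than two weeks, above 8x, above 3x with bilirubin above 2x or INR above 1.5, and above 3x with symptoms. Assumed throughout: normal baseline, no Gilbert's syndrome, ALP not above 2x ULN, and raised bilirubin mainly conjugated.

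**Step 1: mirrored profiles** (enzymes and bilirubin in multiples of ULN).

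| ALT | AST | Bilirubin or INR | Table 16-1 | Table 16-2 |
|---|---|---|---|---|
| 4 | 2.5 | bilirubin 2.5 | potential Hy's Law | bilirubin/INR row: discontinue |
| 2.5 | 4 | bilirubin 2.5 | potential Hy's Law | no row |
| 4 | 2.5 | INR 1.8 | INR trigger | bilirubin/INR row: discontinue |
| 2.5 | 4 | INR 1.8 | INR trigger | no row |

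When ALT leads, 2 of 2 triggers reach the discontinue action. When AST leads, 0 of 2 match any row.

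**Step 2: why this is general.** The lowest ALT threshold in any normal-baseline row of Table 16-2 is 3x ULN. A participant with ALT at or below 3x ULN therefore fails every row, whatever the AST, bilirubin or INR. Conversely, ALT above 3x ULN with bilirubin above 2x ULN or INR above 1.5 always meets the bilirubin/INR condition.

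A grid confirms this, with ALT at 1, 2, 3, 3.5, 6, 9; AST at 1, 3, 3.5, 6, 9; bilirubin at 1, 1.8, 2.5, 4, 11; INR at 1, 1.6; and symptoms absent or present. Of the 5 x 2 = 10 bilirubin and INR pairs, 8 meet a trigger condition.

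- ALT above 3: 3 x 5 x 8 x 2 = 240 trigger combinations, and all 240 reach discontinuation.
- ALT at or below 3 with AST above 3: 3 x 3 x 8 x 2 = 144 trigger combinations, and none of the 144 matches a Table 16-2 row.

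The counts depend on the grid chosen; the all-or-none split does not.

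**Step 3: does other visible text supply the stop?**

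- Section 9.1.1 sends liver events back to Appendix 1. Otherwise it requires stopping when the investigator judges that continuing would harm the participant or that an adverse event puts the participant at risk.
- Section 10.2.1 makes both interruption and discontinuation a question of what is appropriate.
- Section 14.1 expects immediate action where safety requires it, again by judgement.
- Table 16-3 covers isolated bilirubin elevation, which a case with AST above 3x ULN is not.
- Visible Section 17.1 text contains no liver rule, and Table 17-4 lists only thyroid and endocrine tests.

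**Step 4: the references in 10.2.1.** Read literally, follow-up covers only events defined in Table 16-2, which leaves the AST-led case outside. Definitions are placed in the wrong appendix, and the table named for actions does not apply to this case.

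**The case against.** **It may be deliberate.** A sensitive trigger on either enzyme with a narrower mandatory stop on ALT would be coherent, since AST also rises from non-hepatic causes. But the action table's title includes AST, and nothing in the documents explains leaving it out of the rows.

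**Safeguards exist.** This stands. The protocol does not bar stopping: Sections 9.1.1, 10.2.1 and 14.1 allow or require it on judgement, and the DMC reviews unblinded safety data (9.3). A reader might infer that such a participant need never be discontinued. The documents support only the absence of an automatic laboratory-based stop.

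**Scope.** This also stands, in three respects.

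- A case with AST 10x and ALT 4x ULN does reach the discontinue row; the gap needs ALT at or below 3x ULN.
- A reader might extend the point to the elevated-baseline row. But both combined triggers sit under normal baseline, and Table 16-1 has no Hy's Law or INR combination for abnormal baseline.
- A reader might also infer from 10.2.1 and the Grade 2 row of Table 16-3 that the protocol tells sites to keep dosing an AST-led case. The title of Table 16-3 limits it to isolated elevation, so it does not govern this case.

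**Reading and redaction.** In the extracted text the discontinue action sits beside the symptom row. The Amendment 02 log, used only to read that merged cell, shows that it also covers ALT rises with bilirubin rises. Parts of Section 17.1 are redacted, and Section 4.1 says cohort modules can hold their own stopping rules, so a cohort rule cannot be excluded.

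**Practical weight.** The affected group is narrow, and the SAP (2.5.4) records early termination with a single cohort. That reduces how many participants the gap could affect. It does not make the text consistent.

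**Conclusion.** The point holds for the visible core protocol. With normal baseline tests, AST above 3x ULN and ALT at or below 3x ULN, both combined triggers in Table 16-1 can be met without matching any Table 16-2 row. The ALT-led mirror of each must discontinue. What is missing is a mandatory rule; investigators remain free, and in some circumstances obliged, to stop on judgement. The references in 10.2.1 compound the gap by misplacing the definitions, narrowing the follow-up scope and naming a table that does not apply.

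The conclusion rests on reading the merged action cell as covering the bilirubin/INR rows, and on there being no rule in the redacted cohort text. The documents give no frequency of AST-led cases, so the number of participants affected cannot be stated.

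**What to change.** 1. In the normal-baseline Table 16-2 row that carries the bilirubin/INR condition, set the threshold at ALT or AST above 3x ULN, with discontinuation of study drug as the action. Change ALT to ALT or AST in the group heading as well.
2. If the sponsor wants the AST bilirubin arm no wider than the Table 16-1 trigger, add its qualifiers: mainly conjugated bilirubin and ALP not above 2x ULN.
3. In Section 10.2.1, cite Table 16-1 in Appendix 1 for the definitions and the follow-up scope, Table 16-2 for transaminase actions, and Table 16-3 for isolated bilirubin elevation only.

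Whether to add AST to the elevated-baseline, symptom and isolated-elevation rows is for the sponsor to decide.

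The cost is a short protocol amendment under Section 14.1. No tests are added: AST, ALP, direct bilirubin, creatine kinase and PT/INR are already in Table 8-3. The downside is an occasional extra discontinuation when AST rises from a non-hepatic source while bilirubin or INR is raised for another reason. Creatine kinase helps to recognise a muscle source. Without the qualifiers in item 2, the rule would also stop some participants whose bilirubin rise is unconjugated or cholestatic.
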